9.3.1. Dose Reduction

The dosing of Acthar should be tapered from 3x/week to 2x/week for safety reasons if a subject meets any of the following criteria:

- Development of accelerated hypertension (defined as systolic blood pressure \geq 180 *and* diastolic blood pressure \geq 100 mm Hg) that cannot be managed with adjustment of concomitant medications such as antihypertensive medications.
- Development of an edema score of 4 at any visit that cannot be managed with adjustment of concomitant medications such as diuretics (see [Section 24.2](#)).
- Development of congestive heart failure that cannot be managed with adjustment of concomitant medications such as diuretics and antihypertensive medications.
- Development of diabetic signs/symptoms (ie, HbA1c > 8%, or fasting plasma glucose > 126 mg/dL, or classic symptoms of hyperglycemia with random plasma glucose > 200 mg/dL).
- Development of any other AE of at least moderate intensity that cannot be managed with adjustment of concomitant medications.

Any subject whose dose is tapered for any of the reasons described above will have a Taper Safety Visit scheduled 2 weeks after the start of the taper.

9.3.2. Treatment Discontinuation

Treatment with Acthar should be discontinued for safety purposes if the reduction in dosing to 2x/week **and** adjustment of concomitant medications does not manage the following:

- Persistent accelerated hypertension (defined as systolic blood pressure ≥ 180 *and* diastolic blood pressure ≥ 100 mm Hg).
- Persistent edema score of 4 (see [Section 24.2](#)).
- Persistent congestive heart failure.
- Persistent diabetic signs/symptoms (ie, HbA1c $> 8\%$, or fasting plasma glucose > 126 mg/dL, or classic symptoms of hyperglycemia with random plasma glucose > 200 mg/dL).
- Any other AE of at least moderate intensity that cannot be managed with adjustment of concomitant medications.

The investigator should discontinue subjects for safety purposes any time during the study if the subject meets any of the following criteria:

- Development of unexplained and sustained (2 consecutive visits) worsening of disease defined as unresolved progression or 30% decline in eGFR from baseline, or if the subjects remains at significant risk of sequelae of nephrotic syndrome (such as serum albumin < 2.8 mg/dL) and sustained worsening of uPCR (increase $> 50\%$ from baseline).
- Development of ESRD and requirement for chronic renal replacement therapy.
- Administration of live or live-attenuated vaccines after Screening Visit/Visit 1.
- Diagnosis of a malignancy or lymphoproliferative disorder.
- Pregnancy during the course of the study.
- Development of an independent disease that requires treatment with immunosuppressive therapy or plasma exchange therapy.
- Development of a contraindication to IMP use.
- Use of any investigational drug, device, or procedure as part of a research study.

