Eighty percent of cases of FSGS are primary and the incidence of primary FSGS has dramatically increased over the past 20 to 30 years ([D'Agati et al, 2011](#)). Primary FSGS is usually a progressive disorder with a low likelihood of spontaneous remission. Approximately 50% of patients will reach end stage renal disease (ESRD) over a period of 5 to 8 years from the time of biopsy if either unresponsive to treatment or not treated ([Korbet, 1999](#)). Five to 10 percent of all pediatric and adult patients who progress to ESRD will have FSGS as their primary cause of renal failure ([Malaga-Diequez et al, 2015](#)). The prognosis of patients with primary FSGS is best predicted by the severity of proteinuria and the response to therapy. Patients who undergo a complete remission (CR) or partial remission (PR) have a much better chance of renal survival, 80% or greater over a 10-year period, than those who are unresponsive ([Trojanov et al, 2005](#)).

The goal of therapy is to induce CR of proteinuria that in turn leads to the preservation of renal function. The achievement of PR or even substantial reductions in proteinuria translates into less rapid loss of renal function. Adult patients with primary FSGS who have nephrotic range proteinuria are usually treated with renin angiotensin system blockade and immunosuppressive

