4. OBJECTIVES

4.1. Primary Objective

Primary Objective	Primary Endpoints
To confirm the safety and tolerability of Acthar in the induction of remission of proteinuria in subjects with primary FSGS who are resistant to, or intolerant of, at least 1 prior immunosuppressive therapy	
 ● Severity and frequency of adverse events (AEs) ● Changes in physical findings ● Changes in clinical laboratory findings ● Changes in vital signs

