12. STATISTICAL METHODS AND PLANNED ANALYSIS

12.1. General Considerations

Data will be listed, analyzed, and included in the clinical study report. Data will be analyzed as described in the statistical analysis plan. Descriptive statistics for continuous variables will include number of values, mean, SD, median, minimum, and maximum, unless otherwise noted. Frequency and percentages will be calculated for categorical variables. All statistical significance testing will be 2-tailed using $\alpha = 0.05$, unless otherwise specified. Data summary and analyses will be performed with SAS 9.2 or higher.

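### Section 9.3.2 ends participation for sustained worsening in the same kinds of measurement that form the 'changes in' primary endpoints, and the plan has no summary of those endpoints covering all dosed subjects

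*Combined protocol and SAP*

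**What the plan says.** Section 4.1 names four primary endpoints. Besides adverse events they are "Changes in physical findings", "Changes in clinical laboratory findings" and "Changes in vital signs". None has a time point or a summary measure.

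Section 9.3.2 has two groups of discontinuation rules.
- The first follows a failed dose reduction: "Treatment with Acthar should be discontinued for safety purposes if the reduction in dosing to 2x/week", together with adjustment of other medication, does not control the problem. It covers blood pressure ("Persistent accelerated hypertension (defined as systolic blood pressure" at least 180 and diastolic at least 100 mm Hg), edema score 4, congestive heart failure, HbA1c above 8% or glucose limits, and other adverse events of at least moderate intensity.
- The second applies at any time and includes "Development of unexplained and sustained (2 consecutive visits) worsening of disease defined as unresolved progression or 30% decline in eGFR from baseline" and end-stage renal disease (ESRD) needing chronic renal replacement.

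Section 14.1 treats a Section 9.3.2 discontinuation as leaving the study. Section 8.16 then provides one visit, 4 weeks after the last dose.

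On analysis, Section 12.1 gives a general default: "Descriptive statistics for continuous variables will include number of values, mean, SD, median, minimum, and maximum, unless otherwise noted". Section 12.4 speaks of summarizing the general safety profile, but Sections 12.7.2, 12.7.3 and 12.7.4 each provide only a data listing. Section 12.6.4 summarizes discontinuations by reason, and Section 12.7.1 summarizes adverse events leading to discontinuation, both for all dosed subjects.

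**The concern.** A subject whose blood pressure, edema, glucose control or kidney function worsens and stays worse leaves the visit schedule because of that worsening. The missing later values are therefore related to the outcome, and they are missing on the harmful side. The plan does not say how such a subject enters a 'change' endpoint.

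The primary objective is to confirm safety and tolerability in about 60 subjects without a control arm. If the study report adds the obvious table, mean change by visit on the values present, the later rows will look more stable than the dosed group was. If it adds nothing, three of the four primary endpoints have no summary, only listings.

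**Working it through.** **Reading the rules against the endpoints.** Blood pressure is a vital sign (Section 10.5). Edema is part of every physical examination (Section 10.4). HbA1c, glucose and creatinine are listed laboratory tests (Attachment 1). eGFR is not named there, but Section 6.1 calculates it at entry by the MDRD equation. Each limit therefore acts on a measurement that belongs to, or derives from, a 'changes in' endpoint.

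**No stated figure to reproduce.** The sample size of about 60 has no calculation behind it (Section 12.9), and the plan gives no dropout rate or SD. What follows only indicates scale.

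**Slopes for the eGFR rule.** Section 3.1 states: "Approximately 50% of patients will reach end stage renal disease (ESRD) over a period of 5 to 8 years" from biopsy, if unresponsive or untreated. Assume a starting eGFR of 60 and a typical non-remitter who reaches 15 after T years. The log-slope is −ln(60/15)/T = −1.386/T, that is −0.277, −0.213 and −0.173 per year for T = 5, 6.5 and 8. Let 29% remit (7 of 24, the largest series in Section 3.1) with mean slope zero.

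Assumptions not in the documents: the starting value of 60, reading ESRD as eGFR 15, a between-subject SD of log-slope of 0.1, 0.2 or 0.3 per year, and an assay CV of 6% or 10%. Laboratory visits are at Weeks 4 to 24 and 30 to 50 as in Table 1. A subject is removed at the second consecutive laboratory visit with a decline of 30% or more.

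The standard error (SE) of the Week 50 mean is the SD of change in retained subjects divided by √(60 × proportion retained). Results:
- Across all scenarios, about 1% to 24% are removed before Week 50. The Week 50 mean is more favourable by about 0.2 to 2.4 SE.
- Middle case (T = 6.5, SD 0.2): about 11% to 14% removed (0.11 × 60 = 6.6 to 0.14 × 60 = 8.4 subjects). Mean change is about −11% in all dosed against −6% to −8% in those retained, or 1.3 to 1.4 SE. The share with a decline of 30% or more is 18% to 20% against 9% to 11%.
- About 6% to 28% of retained subjects had still crossed the 30% line at one visit or more.

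**A second model as a check.** Assume a linear percentage change with a true Week 50 mean of −5%, −10% or −20%, between-subject SD 15 or 25 points and visit noise 8 points. Then 2.7% to 26.0% are removed and the retained mean is 0.9 to 10.6 points more favourable. In the case of mean −10% and SD 25, 15.2% are removed, leaving 60 × 0.848 = 50.9. The SE is 21.9/√50.9 = 3.07, and the shift of 6.7 points is 6.7/3.07 = 2.2 SE. The mildest case gives 0.9/(16.2/√58.4) = 0.4 SE and the most extreme 10.6/(20.3/√44.4) = 3.5 SE.

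**Which all-dosed summary works.** In the second model, the last on-treatment value taken for all dosed subjects gives means within 2.7 points of the full-cohort value, and a share with a 30% decline of 7.7% to 37.3% against the true 7.0% to 35.2%. The worst on-treatment value does less well. A perfectly stable subject measured at 12 laboratory visits has an expected worst change of about −9% (CV 6%) or −14% (CV 10%) from noise alone.

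**The case against.** The case on the other side is substantial, and much of it stands.

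- *A reader might infer that late visits describe only subjects who never crossed a limit.* The documents do not support that. One crossing removes nobody: the first group of rules needs persistence after dose reduction and other adjustments, and the eGFR rule needs an unexplained decline at two consecutive visits. Managed, transient or explained crossings stay in. The simulations ignore the word unexplained, so they overstate eGFR removals.
- *A reader might infer that nothing would reveal the removals.* Sections 12.6.4 and 12.7.1 tabulate them for all dosed subjects, and clinically significant findings are recorded as adverse events. These tables repair the adverse-event endpoint. They give neither the size of change nor a count per limit, so they do not repair the other three.
- *A reader might infer that a biased by-visit table is planned.* It is not; listings are. The bias is conditional on such a table being produced.
- *A reader might worry that values driven by dialysis would distort the changes.* A constant hazard applied to the figure in Section 3.1 gives 1 − 0.5^((50/52)/T) = 12.5% (T = 5) or 8.0% (T = 8) reaching ESRD in 50 weeks. That figure runs from biopsy in unresponsive or untreated patients, while entry here requires eGFR of at least 30. Under the slopes above only 0% to 0.4% reach eGFR 15 by Week 50, so this part is negligible.
- The size rests on assumptions, only eGFR is quantified, and Section 12.1 defers detail to an analysis plan whose separate text is not in the document reviewed. It may already settle some of this.

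**Conclusion.** The point holds in a limited form. Discontinuation depends on the kinds of measurement that make up three primary endpoints, scheduled follow-up then stops, and the readable plan has no all-dosed summary of those endpoints. A by-visit summary of observed values would under-represent sustained worsening. The direction is clear; the size is not. Under assumed inputs the eGFR rule alone shifts the Week 50 mean by about 0.2 to 2.4 SE in one model and 0.4 to 3.5 SE in another. In the middle case of the first model it roughly halves the observed share with a 30% decline. No figure is offered for blood pressure, glucose or edema. This is an inexpensive improvement to the analysis. It does not show that the safety results would be hidden or invalid.

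**What to change.** In Sections 12.7.2 to 12.7.4 and the analysis plan, for all dosed subjects:
1. Report the number and percentage ever meeting each measured limit in Sections 9.3.1 and 9.3.2, counting removal for a limit as having met it. The fasting-glucose limit can be counted only where fasting status is known, because Section 10.7 allows samples in either state.
2. Report change from baseline to the last on-treatment value. Give worst on-treatment change as supportive only, because measurement noise inflates it.
3. Label Early Termination values as off-treatment.
4. Exclude values after the start of renal replacement from change summaries and count those subjects under item 1.
5. Beside any by-visit summary, show the cumulative number removed under Section 9.3.2.

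No stopping or dosing rule changes, and no new data are collected. The cost is some wording, a few more tables, and summaries that look somewhat less favourable.

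### Section 9.3.2: the albumin example has an impossible unit, and no text says whether the contraindication stop or the reduce-then-stop pathway governs uncontrolled hypertension and NYHA III-IV heart failure

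*Combined protocol and SAP*

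**What the plan says.** **Dose reduction (9.3.1).** Dosing goes from three times to twice weekly on any of several events. Two matter here:

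- "Development of accelerated hypertension (defined as systolic blood pressure" at or above 180 with diastolic at or above 100 mm Hg, where medication changes cannot manage it.
- "Development of congestive heart failure that cannot be managed with adjustment of concomitant medications", with no NYHA class given.

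A subject tapered for such a reason "will have a Taper Safety Visit scheduled 2 weeks after the start of the taper". Section 5.1 keeps a tapered subject at twice weekly for the rest of the study.

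**Discontinuation, first list (9.3.2).** The lead-in is "Treatment with Acthar should be discontinued for safety purposes if the reduction in dosing to 2x/week", together with medication adjustment, does not manage the event. The items include persistent accelerated hypertension at the same cut-offs and "Persistent congestive heart failure".

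**Discontinuation, second list (9.3.2).** This has its own lead-in: "The investigator should discontinue subjects for safety purposes any time during the study if the subject meets any of the following criteria". It does not require a prior dose reduction. One item is "Development of a contraindication to IMP use". Another covers worsening disease. One limb of that item applies if the subject "remains at significant risk of sequelae of nephrotic syndrome (such as serum albumin" below 2.8 mg/dL) and uPCR shows a sustained rise of more than 50% from baseline.

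**What counts as a contraindication.** Exclusion Criterion 10 in Section 6.2 is the only list of contraindications to Acthar in the protocol. It is stated to be non-exhaustive. It names current uncontrolled hypertension, with no pressure given, and current heart failure of NYHA class III to IV.

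**The concern.** Both items are stopping rules in a study whose primary objective is safety and tolerability.

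The albumin figure is the only number that tells an investigator what significant risk of nephrotic complications means. Albumin is in the chemistry panel of Attachment 1, which is drawn at most visits, so sites would be comparing real results with a threshold that nobody can cross.

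The second item leaves one event under two rules. Take a subject who develops class III heart failure that medication cannot manage. One site reduces to twice weekly, sees the event come under control, and continues. Another reads the new condition as a contraindication and discontinues. Both can point to protocol text. Disposition by reason (12.6.4) and the summary of treatment-emergent events leading to early discontinuation (12.7.1) would then depend partly on which rule a site followed. About 60 subjects at about 100 sites is 60/100 = 0.6 per site, so these decisions would usually be made by different investigators.

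**Working it through.** The plan gives no figure to reproduce for either item. The check is a unit conversion, a comparison of the texts, and a count of doses.

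**1. Albumin unit.** Input: 2.8 mg/dL (9.3.2). Conversion: 2.8 / 1000 = 0.0028 g/dL. No living subject has such a value, so the example can never be met. If g/dL was meant, the printed threshold is too low by a factor of 1,000. The documents give no albumin reference range, so g/dL is an inference.

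**2. Where the two rules overlap.**

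| Event that medication cannot manage | 9.3.1 and first list of 9.3.2 | Named in Exclusion 10? | Overlap |
|---|---|---|---|
| Heart failure, NYHA III-IV | Reduce, stop if persistent | Yes, by class | Clear |
| Heart failure, NYHA I-II | Reduce, stop if persistent | No | None |
| Systolic at or above 180 and diastolic at or above 100 mm Hg | Reduce, stop if persistent | Uncontrolled hypertension, no threshold | On plain meaning only |

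Sections 9.3.1, 9.3.2 and 14.1 contain no statement of priority. Section 14.1 calls discontinuation under 9.3.2 mandatory, but it cites that section as a whole, including the list that requires dose reduction first.

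**3. Doses at stake, for a subject on three times weekly with an event at Week t.**

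- Contraindication rule: the early-exit taper in Table 5 footnote a is 2 weeks x 2 per week = 4 doses, and 4 x 80 U = 320 U.
- Dose reduction, maximum: twice weekly to Week 50 is 2 x (50 - t) doses.

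| t (chosen for illustration) | Maximum after reduction | Units | Difference from 4 doses |
|---|---|---|---|
| 4 | 2 x 46 = 92 | 7,360 | 88 |
| 24 | 2 x 26 = 52 | 4,160 | 48 |
| 38 | 2 x 12 = 24 | 1,920 | 20 |

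**4. Who these differences apply to.** Continuing to Week 50 is allowed only if twice-weekly dosing plus medication manages the event. If it does not, the first list stops treatment. If that happens at the 2-week Taper Safety Visit, the subject has had 2 x 2 = 4 doses, the same as the exit taper, and the difference is 0. The two routes look identical for the first 2 weeks.

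**The case against.** The strongest answer is that the text already forms one coherent algorithm. Section 9.3.1 and the first list of 9.3.2 name these two conditions and grade the response. The contraindication item would then cover conditions with no pathway of their own, such as ocular herpes simplex or peptic ulcer. If it also covered uncontrolled hypertension, the item on persistent accelerated hypertension would have almost nothing left to do. The contraindication item does not cite Exclusion 10, which is an entry criterion. Section 14.1 also limits withdrawal for meeting an exclusion criterion to conditions not considered adverse events, and these would ordinarily be adverse events.

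Much of this stands. The graded pathway is internally consistent, and it may well be what the sponsor intends. But the protocol nowhere says that the specific rule prevails, and the second list has its own lead-in that is not conditional on the first. For NYHA III-IV heart failure the overlap needs no interpretation once Exclusion 10 is taken as the meaning of contraindication. For hypertension it rests on the ordinary meaning of uncontrolled. The adverse-event route in 14.1 is a real safeguard, but it depends on someone finding the risk unacceptable and does not rank the two rules.

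A reader might infer that the protocol leaves subjects with unmanaged hypertension or heart failure on drug until Week 50. It does not: the first list stops treatment when the reduction fails. A reader might also infer that the albumin slip disables the whole worsening-disease trigger. It does not: the value follows a such-as, and the eGFR limb and the uPCR condition still work.

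**Conclusion.** Both items are wrong as written and together rate minor to should-fix.

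The albumin unit is a plain error. It removes the only numerical guide in one limb of a discontinuation trigger, and the rest of that trigger still operates.

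The dosing item is a missing statement of priority. Its practical effect is confined to a subject whose NYHA III-IV heart failure or accelerated hypertension is managed at twice-weekly dosing: sites can differ on whether that subject stays on drug. For that subject the difference is at most 88, 48 or 20 doses for events at Weeks 4, 24 and 38. The documents give no event rates, so no number of affected subjects can be stated. The Safety Population, defined by receipt of at least one dose, is unaffected.

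The conclusion assumes that Exclusion 10 shows what the protocol means by a contraindication and that pressure at the 9.3.1 cut-offs that medication cannot manage counts as uncontrolled. It does not imply that immediate discontinuation is the right rule. That is a clinical trade-off which the documents do not settle.

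**What to change.** - Correct the albumin unit in 9.3.2, presumably to g/dL, after the sponsor confirms it.
- Add one sentence to 9.3.2 stating which rule governs. Either exempt conditions handled in 9.3.1 from the contraindication item, or state that NYHA III-IV heart failure and uncontrolled hypertension go directly to discontinuation with the 2-week taper of Table 5 footnote a. The sponsor's clinicians should choose the direction.

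Cost: one unit and one sentence at the next amendment, and a memo to sites. No extra subjects, visits or procedures are needed.

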9.4. Description of IMP

Acthar is a highly purified sterile preparation of prolonged-release porcine ACTH analogue in 16% gelatin for intramuscular or SC injection. Acthar contains 0.5% phenol, not more than 0.1% cysteine (added), sodium hydroxide and/or acetic acid to adjust pH, and water for injection. Acthar is obtained from processing porcine pituitary using a FDA approved process.

Acthar is supplied as 5 mL multidose vials. Acthar vials contain 80 U of ACTH per mL. The vials should not be over pressurized prior to withdrawing the product. The vials should be warmed to room temperature before using and will be labeled according to all applicable national and local regulations.

9.5. Storage of Clinical Supplies

IMP will be maintained in a temperature controlled, secure locked area with restricted access at the study site.

IMP will be supplied in kits containing the appropriate amount of vials according to the treatment group to which the subject is assigned. IMP will be stored under refrigeration between 2° to 8°C (36° to 46°F). Please refer to the Pharmacy Manual for complete information regarding storage and accountability of IMP.

